12.2 Study Hypotheses

The primary endpoint is objective response in skin of at least 4 months duration (ORR4).

Response to cobomarsen will be compared to the control group using a Cochran-Mantel-Haenzel (CMH) statistic incorporating the stratification factors from the randomization.

The randomization will be stratified based on subjects with at least one skin tumor at Screening vs. no skin tumors at Screening. Subjects will also be stratified based on prognostic factors (age at diagnosis > 60 years and LDH level > ULN at diagnosis) (Scarlsbrick et al. 2015). Subjects will be stratified based on having 0-1 vs 2 of these prognostic factors.

There is only one primary and one key secondary endpoint (PFS) for analysis; a one-sided $p=0.025$ for response by CMH will establish statistical significance. The study hypothesis is that response to cobomarsen is superior to the control group. The null hypothesis (H_0) is that N (%) of responders to cobomarsen and N (%) of responders to control do not differ; the alternative hypothesis (H_a) is that N (%) of responders to cobomarsen is superior to N (%) of responders to control. A step-down procedure will be used to assess the statistical significance of PFS, such that a statistically significant difference in PFS will be confirmatory of a treatment effect only if the analysis of the primary endpoint is statistically significant at the one-sided 0.025 level of significance.

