12.4.7 Planned Interim Analyses

An interim analysis will be performed after approximately 40 subjects are followed for a minimum of approximately 6 months to allow assessment for a 4-month duration of response (ORR4) from the date of initial objective response. A decision to stop the study at interim analysis for superiority will be considered if the one-sided test statistic p-value is < 0.01 (Pocock, et al. 1977). The number of skin ORR4 events required to demonstrate superiority at the interim analysis are shown in [Table 6](#).

Table 6: ORR4 Events Required to Demonstrate Superiority in Skin Objective Response for Interim Analysis ($p < 0.01$)

Vorinostat (N = 18)	Cobomarsen (N = 18)
0/18	6/18
1/18	8/18
2/18	10/18
3/18	11/18
4/18	12/18
5/18	13/18
6/18	14/18
7/18	15/18
8/18	16/18
9/18	17/18
10/18	18/18
11/18	18/18
12/18	18/18

Enrollment will be halted if data from this study or other cobomarsen studies conclusively demonstrate that cobomarsen does not have significant activity in MF.

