12.5 Sample Size Determination

12.5.1 Primary Endpoint Sample Size

A sample size of 126 subjects (63 per group) provides greater than 80% power to detect a difference between cobomarsen and vorinostat, after accounting for the alpha spend at the interim analysis (interim alpha = 1%, one sided). This power statement assumes a response rate of 35% in the cobomarsen group and 10% in the vorinostat group, using a one-sided, two sample binomial test of proportions at the adjusted final one-sided alpha of 1.5% (total alpha = 2.5%, one sided). The planned primary analysis will account for all randomized subjects. Power was computed using the normal approximation method. When the normal approximation method is used to compute power for Fisher's Exact Test, the results are based on the pooled, continuity-corrected Chi-Square test (i.e. Z-Test C.C. (Pooled)). ([Kim et al. 2017](#)).

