12.5.2 Key Secondary Endpoint Sample Size

The null hypothesis is that there is no difference in progression free survival (PFS) between cobomarsen and vorinostat. A sample size of 126 subjects (63 per group; 66 events) provides at least 80% power to detect a difference between vorinostat and cobomarsen, assuming a median PFS of 4 months for vorinostat and 8 months for cobomarsen. This calculation is based on a one-sided, logrank test at the 0.025 level of significance, assuming 15 months of recruitment, 6 months of follow-up, and 17% censoring. No interim analysis is planned for PFS.

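### PFS can be unlocked by an ORR4 win at either look, but its only stated level is an unsplit 0.025 and no rule covers an interim stop, so its false-positive rate can exceed 2.5%

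*Combined protocol and SAP*

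**What the plan says.** - **Gate (Section 12.2).** "A step-down procedure will be used to assess the statistical significance of PFS, such that a statistically significant difference in PFS will be confirmatory". The condition attached is that ORR4 has first succeeded at one-sided 0.025. The section does not separate an ORR4 win at the interim from one at the final analysis.
- **Interim (Section 12.4.7).** The timing is given as follows: "An interim analysis will be performed after approximately 40 subjects are followed for a minimum of approximately 6 months". On early success the section says: "A decision to stop the study at interim analysis for superiority will be considered if the one-sided test statistic p-value is < 0.01". Section 4.1 suspends enrollment at about 40 subjects until this analysis is complete.
- **Final ORR4 level (Section 12.5.1).** 126 subjects, with a one-sided level of 0.015 left after 0.01 is spent at the interim.
- **PFS (Section 12.5.2).** 126 subjects and 66 events, medians of 4 and 8 months. "This calculation is based on a one-sided, logrank test at the 0.025 level of significance". The section ends: "No interim analysis is planned for PFS".
- **Status of secondary p-values (Section 12.4.4).** They are described as supportive, without an exception for PFS. This conflicts with Section 12.2.

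No section says whether, when, on how many events or at what level PFS is tested if ORR4 stops the trial at the interim.

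**The concern.** Alpha is divided between the two looks for ORR4 but not for PFS. If the study stops on an interim ORR4 win, the trial that remains has about 40 subjects, and any PFS test uses them. If it does not stop, PFS is tested on 126. Each path has one PFS test, but the ORR4 interim result chooses the sample. That result is positively related to PFS in the same subjects: ORR4 needs a response held for 4 months, and confirmed loss of response is itself a progression event (Section 7.5.1.3, Table F2). The small sample is therefore used mainly when chance has already favoured cobomarsen.

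PFS is the only endpoint besides ORR4 that Section 12.2 allows to be confirmatory. The case that matters is one where cobomarsen raises durable skin response but does not delay progression.

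**Working it through.** **1. The plan's own PFS figure.** Under exponential PFS, medians of 4 and 8 months give a hazard ratio of 0.5. Schoenfeld events with 1:1 allocation: 4(z_α + z_β)²/(ln 0.5)².
- At one-sided 0.025 and 80% power: 4(1.960 + 0.842)²/0.4805 = 65.3, so 66. Power at 66 events is 80.4%. The stated figure reproduces.

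**2. ORR4 inputs.** 35% v 10%, 63 per group, pooled rate 22.5%. Expected final z = 0.25/√(2 × 0.225 × 0.775/63) = 3.36 (3.52 with unpooled variance); 3.4 is used below. Interim fraction t = 40/126 = 0.317. The chance of an interim win is 1 − Φ(2.326 − 3.4√0.317) = 34%.

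**3. PFS false-positive rate if 0.025 is used on whichever sample ORR4 leaves.** There is no PFS effect, and every interim win stops the trial. Z₁ and Z₂ are the ORR4 statistics, and S₁ and S₂ the PFS statistics, at interim and final. They are jointly normal, with ORR4-PFS correlation ρ at the same look and √0.317 between looks for the same endpoint. ρ is not in the documents; it is an assumption.

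Rate = A + B, where A = P(Z₁ > 2.326, S₁ > 1.960) and B = P(Z₁ ≤ 2.326, Z₂ > 2.170, S₂ > 1.960).

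| ρ | A, planned ORR4 effect | B, planned ORR4 effect | A + B | Maximum of A + B over ORR4 effects |
|---|---|---|---|---|
| 0 | 0.85% | 1.39% | 2.24% | 2.50% |
| 0.3 | 1.55% | 1.21% | 2.76% | 2.78% |
| 0.5 | 2.01% | 0.99% | 3.00% | 3.02% |
| 0.7 | 2.37% | 0.73% | 3.10% | 3.32% |
| 0.9 | 2.50% | 0.47% | 2.97% | 3.79% |

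If ORR4 also has no effect, the rate is 0.06% to 1.7% over the same correlations, because the gate seldom opens.

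**4. Sensitivity.**
- *Stopping is optional.* Suppose half of interim wins lead to a stop and the rest go on to a PFS test at the final analysis. The rate becomes ½A + ½C + B with C = P(Z₁ > 2.326, S₂ > 1.960). At ρ = 0.5, C = 1.50%, giving 1.01 + 0.75 + 0.99 = 2.75%. With no stops, C + B = 2.49%.
- *Share of PFS information at the interim.* With 45% to 55% instead of 32%, the planned-effect rate is 2.6-2.7% at ρ = 0.3 and 2.8-2.9% at ρ = 0.5.
- *Patient-level simulation.* No PFS effect, exponential PFS with median 4 or 8 months, ORR4 possible only after 5 or 6 progression-free months, always stopping. Six scenarios of 200,000 trials gave 2.2% to 3.2%, with ORR4-PFS correlations of 0.24 to 0.50.
- *Gate level.* Using 0.025 instead of 0.015 for the final ORR4 gate moves the maxima by about 0.01 percentage points.

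**5. Events on the early path.** Forty subjects cannot give 66 events. With the plan's medians, accrual over 15 × 40/126 = 4.8 months and 6 months of further follow-up, about 25 are expected.

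**6. Rates under the two remedies.** One PFS test at a fixed final analysis has error of at most 2.5%. A 0.01/0.015 split is bounded by 0.01 + 0.015 = 0.025; its computed maximum is 1.2% to 1.9% for ρ from 0 to 0.9.

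**The case against.** The strongest reply is that the plan describes only one PFS test, at the end. Section 12.5.2 ties 0.025 to 126 subjects and 66 events and rules out a PFS interim. Section 12.1 places the final analysis after the last subject completes or discontinues, and further detail is left to an SAP due before database lock. On that reading the PFS error is at most 2.5%. This stands for a trial that runs to 126. It does not cover a trial stopped at the interim, where the last subject is one of about 40 and the final analysis is of a sample the ORR4 result selected. Section 12.1 also allows extra database locks according to endpoint timing.

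A reader might infer that the plan prescribes a 0.025 PFS test at the interim and that the true error is 3.0-3.3%. The documents support neither. Testing PFS after an early stop is an inference, stopping is only to be considered, and the correlation is not given. The figure also needs a substantial ORR4 benefit with exactly no PFS benefit, which strong error control must cover but which is unfavourable.

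Given an interim win, the false PFS claim rate is higher (A divided by 34%: about 4.5% at ρ = 0.3 and 7.0% at ρ = 0.7). The plan does not undertake to control that conditional rate, so it should not be set against 2.5%.

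**Conclusion.** The point holds as a gap in the rule, with a modest and conditional consequence. The step-down and the single PFS level, as written, do not guarantee 2.5% once an interim ORR4 win can end the trial. With no PFS effect and a stop after every interim win, the rate can reach about 2.8% at correlation 0.3 and 3.0-3.3% at 0.5-0.7. These are maxima over the ORR4 effect, but at the planned 35% v 10% the rate is already 2.8% to 3.1% over those correlations. The excess is therefore roughly 0.3 to 0.8 percentage points. It disappears at zero correlation, if ORR4 also has no effect, or if PFS is tested only at one fixed final analysis. It is smaller when some interim wins do not stop the trial.

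Section 12.2 quotes 0.025 for ORR4 where Section 12.5.1 leaves 0.015 at the final analysis. That is a separate inconsistency about the ORR4 error and does not drive the PFS figures here.

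**What to change.** **Preferred.** In Sections 12.2 and 12.5.2, before interim data are seen, state that PFS is tested confirmatorily once, at one-sided 0.025, only at the planned final analysis of the 126-subject trial, and only if ORR4 has succeeded. If the study stops at the interim for ORR4, PFS is reported as supportive. Amend Section 12.4.4 so that its statement on secondary p-values excepts PFS on the 126-subject path. This takes a sentence or two and leaves the planned PFS level, events and power unchanged. The loss is a confirmatory PFS claim on the path with about 40 subjects, which cannot reach 66 events anyway.

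**Conservative alternative.** Give PFS 0.01 after an interim stop or 0.015 at the final analysis, tested once on either path. This keeps a claim on both paths but over-corrects (maximum error 1.2% to 1.9%). Section 12.5.2 would have to restate power at 66 events as Φ(½√66 × ln 2 − 2.170) = 74%. For 80%, 4(2.170 + 0.842)²/0.4805 = 75.5, so 76 events. The plan's medians, 15 months of recruitment and 6 months of follow-up imply about 97 events, or 97 × 0.83 = 81 if the 17% censoring is taken off proportionally. Power at 0.015 would then be about 83% to 89%, provided the analysis waits for those events.

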The analysis of the primary efficacy endpoint is the proportion of subjects in the randomized period achieving an ORR4 in skin by mSWAT assessments. The statistical test for the primary efficacy endpoint will be one-sided and will be split between the interim and final analysis and conducted using a total 0.025 significance level. Additional details of the primary efficacy endpoint in addition to the secondary efficacy endpoints will be detailed in the statistical analysis plan.

	
Safety analyses will include AEs, concomitant medications, laboratory data, physical examination, and ECG data.
 
The following analysis populations will be defined:
 
Intent to Treat Analysis Set (ITT)
 
The ITT will include all randomized subjects who received at least one dose of study treatment (cobomarsen or vorinostat) and had at least one post-baseline assessment.
 
Safety Set
 
The Safety set will include all randomized subjects who received at least one dose of study treatment (cobomarsen or vorinostat).
 
Per Protocol Set (PPS)
 
The PPS will consist of all subjects randomized to the study, who received study treatment, and completed assessments necessary for the evaluation of the primary endpoint with no major protocol deviations that would affect endpoint analysis.
 
Pharmacokinetic Analysis Set (PKAS)
 
The PKAS will consist of subjects randomized to cobomarsen who received at least one dose of cobomarsen and had at least one post baseline PK sample taken and analyzed.

Sample Size Justification:
	
Total enrollment of approximately 126 subjects randomized 1:1 provides greater than 80% power to detect a 25% difference (35% vs 10%) in the primary outcome, ORR₄, between the investigational product and active comparator groups.

Planned Interim Analysis:
	
An interim analysis will be performed after approximately 40 subjects are followed for a minimum of approximately 6 months.

Trial-specific Committees:
	
Data Monitoring Committee
 
The Data Monitoring Committee (DMC) will be responsible for reviewing safety data at regular intervals as well as to perform the interim analysis for futility. A separate DMC Charter will be established that outlines DMC membership, precisely what data will be reviewed, along with the timing and frequency of the reviews. DMC recommendation will be provided to the Sponsor in compliance with the DMC Charter.

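### Section 12.2 tests ORR4 and gates PFS at an unadjusted one-sided 0.025, while the rest of the protocol splits that total into 0.01 at the interim and 0.015 at the final analysis

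*Combined protocol and SAP*

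**What the plan says.** Section 12.2 (Study Hypotheses) says that a one-sided p=0.025 "for response by CMH will establish statistical significance". The same paragraph makes PFS the step-down endpoint, confirmatory "only if the analysis of the primary endpoint is statistically significant at the one-sided 0.025 level of significance". It refers to neither an interim analysis nor a level for a particular look.

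Three other places treat 0.025 as a total:

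- **Synopsis, Statistical Methods:** the one-sided test "will be split between the interim and final analysis and conducted using a total 0.025 significance level". The component levels are not given.
- **Section 12.4.7:** "A decision to stop the study at interim analysis for superiority will be considered if the one-sided test statistic p-value is < 0.01". No final level is given.
- **Section 12.5.1:** an interim alpha of 1%, with power computed "at the adjusted final one-sided alpha of 1.5% (total alpha = 2.5%, one sided". This is the only place that states 0.015.

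For PFS, section 12.5.2 uses a one-sided logrank test at 0.025 and adds "No interim analysis is planned for PFS".

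The purpose of the interim look is also described in two ways. The synopsis paragraph on the Data Monitoring Committee asks it to review safety data "as well as to perform the interim analysis for futility". Section 12.4.7 sets a superiority boundary with event counts (Table 6), and separately halts enrollment if data "conclusively demonstrate that cobomarsen does not have significant activity in MF".

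**The concern.** Section 12.2 is where a reader looks for the rule that decides whether the trial succeeded. As worded, it compares the CMH p-value with 0.025 whatever has happened before. The only statement of the stricter final level sits in the sample-size section.

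Two conclusions depend on the choice: whether ORR4 is met, and whether the PFS result is confirmatory. The trial is open-label with an interim look at ORR4, and the SAP need only be complete before database lock. The threshold could therefore still be unsettled when the data are already partly known. If the looser rule is used at the final analysis, the 0.01 spent at the interim comes on top of a full 0.025.

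**Working it through.** **1. The plan's own figures.** Inputs from 12.5.1: 63 per arm, 35% vs 10%, interim 0.01, final 0.015, pooled continuity-corrected normal approximation.

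- Alpha: 0.01 + 0.015 = 0.025, as stated.
- Power = Φ[(d − cc − z·SE0)/SE1], with d = 0.25 and cc = 1/63 = 0.0159.
- SE0 = √(0.225 × 0.775 × 2/63) = 0.0744. SE1 = √(0.35 × 0.65/63 + 0.10 × 0.90/63) = 0.0710.
- At 0.015, z = 2.170: (0.2341 − 0.1615)/0.0710 gives 1.02, so power is 84.7%. At 0.025 it would be 89.3%.

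The claim of more than 80% holds at the split level, so 126 subjects do not depend on the looser rule.

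**2. Overall type I error, normal approximation.** Total = 1 − Φ2(c1, c2; ρ), where c1 = 2.326 (0.01 interim), c2 = 2.170 (0.015) or 1.960 (0.025), and ρ = √t. The information fraction t is 40/126 (ρ = 0.563), from about 40 subjects at the interim, or 36/126 (ρ = 0.535), from 18 per arm in Table 6.

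| Final level | t = 40/126 | t = 36/126 |
|---|---|---|
| 0.015 (12.5.1) | 0.0229 | 0.0231 |
| 0.025 (12.2 read literally) | 0.0321 | 0.0323 |

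**3. Overall type I error, exact enumeration.** The model has 18 per arm at the interim, with a stop if the Table 6 counts are reached, and then 63 per arm at the final. The final test is an unstratified pooled score test, an assumption standing in for the stratified CMH test. Common response rates run from 10% to 35% in 1-point steps.

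- The Table 6 boundary spends only 0.1% to 0.5%, less than the nominal 1%.
- Final at 0.025: total 2.54% to 2.89% (2.60% at a 10% rate).
- Final at 0.015: total 1.59% to 1.93%.
- If the interim uses an uncorrected score test at 0.01 in place of the table: 2.86% to 3.45% with the final at 0.025.

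**4. Results that fall between the two rules.** Score statistic: z = (difference in proportions)/√(p̄(1 − p̄) × 2/63).

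- 13 vs 5 responders: (8/63)/0.0623 = 2.04, one-sided p = 0.021.
- 16 vs 7 responders: (9/63)/0.0688 = 2.08, one-sided p = 0.019.

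Both succeed under 12.2 and fail under 12.5.1.

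**5. How often it would matter.** In the model of step 3, P(success with final 0.025) − P(success with final 0.015) is:

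- 35% vs 10%: 2.9%
- 30% vs 10%: 5.8%
- 25% vs 10%: 8.0%

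**6. PFS level.** Medians of 4 and 8 months give a hazard ratio of 0.5. Events = 4 × (1.960 + 0.842)²/(ln 0.5)² = 65.3, rounded up to 66. This matches 12.5.2 at one-sided 0.025, so the PFS test's own level is internally consistent.

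**The case against.** The best defence is that 0.025 in 12.2 is simply the overall level. The synopsis and 12.5.1 both call 0.025 the total, significance at the 0.025 level is ordinary wording for a group-sequential design, and detail is deferred to the SAP. The sections can then be read together, and what is missing is a cross-reference. This reading is possible, and the gate sentence alone would bear it. The ORR4 sentence fits it less well, because it gives 0.025 as the p-value that establishes significance. Even read charitably, 12.2 supplies no usable rule for either look.

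The second objection is that the harm is small and depends on the test. That is partly right. The 3.2% assumes the interim spends its full 0.01, and the exact excess is modest. With Fisher's exact test or a continuity-corrected chi-square at the final analysis, the literal rule stays between 1.2% and 2.0%, and the two examples give Fisher p-values of 0.036 and 0.032, which fail both thresholds. But 12.2 names CMH for the analysis; Fisher and the correction appear only in the power calculation. Whichever test is used, p-values between 0.015 and 0.025 remain in dispute.

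Third, the protocol does not say when PFS would be tested if the study stopped early for ORR4. That is true but separate. It does not disturb the 0.025 level for a PFS test done once, which is what 12.5.2 plans.

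**Conclusion.** The point holds: the success rule in 12.2 is wrong as written and needs correcting. Its importance comes from two sections giving different answers on the primary endpoint and on the status of PFS, more than from the size of the alpha excess.

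That excess is conditional on applying 12.2 literally at the final look: about 3.2% against a stated 2.5% by normal approximation, and 2.5% to 2.9% in the exact check. The exact figures rest on Table 6 as the interim boundary, an unstratified score test in place of CMH, and common rates of 10% to 35%. The sponsor's own split controls the error in both calculations, at about 2.3% and at 1.6% to 1.9%. The disputed outcome is most likely when the true effect is smaller than planned.

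The futility wording in the synopsis is a minor inconsistency with no bearing on alpha.

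**What to change.** In 12.2, replace both 0.025 figures with the levels already specified: ORR4 is significant if one-sided p<0.01 at the interim or p<0.015 at the final analysis, for a total of 0.025. State that PFS is tested as confirmatory only if ORR4 crosses the boundary for its look. The 0.025 level for PFS in 12.5.2 can stay, since no interim PFS test is planned. Amend the synopsis paragraph on the Data Monitoring Committee so that it describes both the superiority boundary and the lack-of-activity provision of 12.4.7.

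The cost is wording in 12.2 and one phrase in the synopsis. The final ORR4 hurdle becomes stricter than 12.2 now states, but it is the one used in 12.5.1, where power is 84.7%. Sample size, patients and procedures are unaffected.

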12.3 Analysis Datasets

Assignment of subjects to analysis sets will be done prior to database lock. The following analysis sets will be defined: the Intent to Treat analysis set (ITT), the Safety set, the Per Protocol Set (PPS), and the PK Analysis Set (PKAS).

12.3.1 Intent to Treat Analysis Set (ITT)

The ITT will include all randomized subjects who received at least one dose of study treatment (cobomarsen or vorinostat) and had at least one post-baseline assessment.

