4.1 Randomized Period

Approximately 126 subjects are expected to be enrolled. An interim analysis will be conducted after approximately 40 subjects have been followed for a minimum of approximately 6 months; enrollment will be suspended after approximately 40 subjects have been enrolled until the completion of the interim analysis.

Subjects will be randomized in a 1:1 ratio to receive cobomarsen or vorinostat. Subjects will undergo Screening lasting up to 28 days from the time of informed consent, followed by active treatment, and then follow-up for response and disease progression.

Figure 1. SOLAR Study Design Schematic

Subjects will remain on their assigned study treatment until one of the following occurs:

1. Disease progression, defined as either (see [Appendix F](#)):
 - a. Confirmed progression in skin
 - b. Clinical progression in other compartments, documented by assessments (flow cytometry and/or CT scan) completed per investigator discretion
 - c. Partial or complete skin response followed by a confirmed loss of skin response as defined by an increase of mSWAT of greater than the sum of nadir plus 50% baseline score.

Progressions based on mSWAT will be confirmed by repeated measurement 28 days (± 3 days) after the first determination of progression.

If confirmed, the date of progression will be based on the first determination of progression. Subjects will continue the study treatment until disease progression is confirmed.

2. Subject meets one of the other treatment discontinuation criteria (see [Section 5.4.1](#)).

Safety assessments will include monitoring the incidence and severity of AEs and SAEs, physical examination findings, vital signs, ECG monitoring, and clinical laboratory assessments.

Samples will be collected for PK in the cobomarsen group on Days 1, 2, 3, 5, 8, 15, 29, and every 4 weeks from Weeks 9 through 81, every 8 weeks thereafter, and at the follow-up/end of treatment visit.

mSWAT evaluations will be completed on Days 1 and 29, every 4 weeks through Week 81, every 8 weeks thereafter, and at the End of Treatment and Follow-up visits. Every effort will be made to perform a final disease assessment for subjects who withdraw from the study early.

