8.2.1 Day 1 (First Day of Study Treatment)

- Perform CTCL disease evaluation using the mSWAT (predose) (see [Appendix F](#)).
- Obtain vital signs (blood pressure, heart rate, respiratory rate, and body temperature).
- Perform a complete physical examination (including documentation of weight). May be performed within 2 days prior to the Day 1 visit.
- Collect blood for the following:
 - Complement C5a, Bb testing (cobomarsen predose and within the 10 minutes before the end of the infusion) (vorinostat predose and 2 hours post dose);
 - Hematology (predose);
 - Clinical chemistry (predose);
 - TSH (predose);
 - Coagulation (predose and at 3 hours [\pm 10 minutes] postdose);
 - Cobomarsen group only: PD and ADA (predose);

- Cobomarsen group only: PK (pre-dose, 60 ± 5 minutes after the start of the infusion, 5 ± 5 minutes before the end of the infusion, and 4 hours [± 10 minutes] after the end of the infusion).
- Collect urine for the following:
 - Urinalysis (predose; only if Screening measurement was performed > 3 days before Day 1);
 - Pregnancy test (predose, for females of childbearing potential).
- Perform a single 12-lead ECG
 - Cobomarsen group only: Predose and as soon as possible postdose, ideally within 30 minutes of the end of infusion.
- Vorinostat group only: Predose and 1 ± 0.5 hours postdose.
- IWRS Transaction (Study Treatment Dispensation).
- Cobomarsen group only: Administer intravenous infusion of cobomarsen with vital signs performed within 15 minutes of the end of the infusion and keep the subject in the clinic for 4 hours for observation.
- Vorinostat group only: Administer first dose in the clinic with food following collection of laboratory samples and keep the subject in the clinic for 4 hours for observation.
- Instruct subjects to record daily dosing in the provided diary (vorinostat group only).
- Review and record AEs and concomitant medications.

8.2.2 Day 2

- Obtain vital signs (blood pressure, heart rate, respiratory rate, and body temperature).
- Collect blood for the following:
 - Complement C5a, Bb testing (24 ± 4 hours) (predose for vorinostat);
 - Coagulation (predose for vorinostat);
 - Cobomarsen group only: PK (24 ± 4 hours after Day 1 dosing).
- Vorinostat group only: Administer the dose in the clinic with food following collection of laboratory samples.
- Instruct subjects to record daily dosing in the provided diary (vorinostat group only),

- Review and record AEs and concomitant medications.

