12.3.3 Per Protocol Set (PPS)

The PPS will consist of all subjects randomized to the study, who received study treatment, and completed assessments necessary for the evaluation of the primary endpoint with no major protocol deviations that would affect endpoint analysis.

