12.4.3 Analysis of the Primary Efficacy Endpoint

The analysis of the primary efficacy endpoint is the proportion of subjects in the randomized period achieving an ORR4 in skin using mSWAT assessments. ORR4 is the proportion of subjects with a CR or PR for 4 consecutive months confirmed by repeat assessments no less than 28 days (\pm 3 days) later ([Olsen et al. 2011](#)).

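### The ITT set excludes some randomized subjects, section 12.5.1 promises a primary analysis of all of them, and no defined set or named primary set reconciles the two

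*Combined protocol and SAP*

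**What the plan says.** Section 12.3.1 limits the ITT set to randomized subjects who "received at least one dose of study treatment (cobomarsen or vorinostat) and had at least one post-baseline assessment". The synopsis repeats this. Neither place says what kind of assessment is meant.

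Section 12.5.1, on the sample size, says: "The planned primary analysis will account for all randomized subjects".

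Section 12.3 lists four sets: ITT, Safety, Per Protocol and PK. The Safety set requires at least one dose. The Per Protocol Set requires treatment and subjects who "completed assessments necessary for the evaluation of the primary endpoint with no major protocol deviations that would affect endpoint analysis". The PK set is confined to dosed cobomarsen subjects.

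Section 12.4.3 describes the primary analysis as the "proportion of subjects in the randomized period achieving an ORR4 in skin using mSWAT assessments", and section 12.4.7 says: "An interim analysis will be performed after approximately 40 subjects are followed for a minimum of approximately 6 months". Neither names an analysis set, nor does section 12.2. Section 12.4.1 states that missing data are not imputed unless otherwise specified.

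**The concern.** Two operative sentences give different denominators for the primary endpoint, and the one that promises all randomized subjects cannot be carried out with any set the protocol defines.

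A subject who was never dosed, or who left before a 4-month response could be observed, cannot be an ORR4 responder. Dropping that subject raises the observed rate in that arm. The trial is open label, so the decision not to start treatment, or to leave early, is made with the allocation known and need not be balanced between a weekly infusion and a daily capsule. Section 12.3 asks only that sets be assigned before database lock, so the reading of the undefined term could be settled after allocation and outcomes are known.

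The same denominator governs the interim superiority decision in section 12.4.7 and, through the step-down in section 12.2, whether PFS can be tested as confirmatory.

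**Working it through.** **1. Does any defined set match section 12.5.1?**

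| Set | Requires dosing | Further conditions |
|---|---|---|
| ITT (12.3.1) | yes | a post-baseline assessment, type not given |
| Safety (12.3.2) | yes | none |
| Per Protocol (12.3.3) | yes | primary-endpoint assessments, no major deviation |
| PK (12.3.4) | yes | cobomarsen arm only, a PK sample |

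None holds all randomized subjects. Undosed randomized subjects are possible, because section 8.1 allows up to 3 working days between randomization and first dose. Section 5.4.2 says subjects who discontinue prematurely are not replaced.

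**2. What does a post-baseline assessment mean?** Read literally, the Day 1 ECG qualifies ("Cobomarsen group only: Predose and as soon as possible postdose, ideally within 30 minutes of the end of infusion"), as do the Day 2 procedures, so essentially only undosed subjects are lost. Read as an mSWAT score, the schedule is "mSWAT evaluations will be completed on Days 1 and 29, every 4 weeks through Week 81, every 8 weeks thereafter". A subject who leaves before Day 29 without an End of Treatment mSWAT (section 8.4) is then lost too.

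**3. The plan's own power figure.** Inputs from section 12.5.1: n = 63 per arm, rates 0.35 and 0.10, final one-sided alpha 0.015 (z = 2.170), pooled test with continuity correction.

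- Pooled rate 0.225; null SE = √(0.225 × 0.775 × 2/63) = 0.0744
- Alternative SE = √[(0.35 × 0.65 + 0.10 × 0.90)/63] = 0.0710
- Power = Φ[(0.25 − 1/63 − 2.170 × 0.0744)/0.0710] = Φ(1.02) = 84.7%

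Without the correction it is 89.4%, and by exact Fisher enumeration 86.7%. All agree with the stated figure of more than 80%.

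**4. Effect of removing non-responders.** The counts are assumptions; the documents give none. Method: enumerate all outcomes of two binomials with 63 per arm, take k non-responders out of the stated denominator, and apply an unstratified one-sided CMH test at 0.015. Power in the last column is at 35% v 10%. It starts from 90.6% rather than 84.7% because this test has no continuity correction.

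| Removed | Type I error, both rates 10% | both 20% | both 30% | Power |
|---|---|---|---|---|
| none | 1.56% | 1.47% | 1.50% | 90.6% |
| 1, cobomarsen only | 1.57% | 1.71% | 1.78% | |
| 3, cobomarsen only | 1.72% | 2.09% | 2.34% | |
| 6, cobomarsen only | 2.18% | 3.09% | 3.56% | 95.0% |
| 3, vorinostat only | 0.95% | 1.05% | 0.95% | |
| 6, vorinostat only | 0.86% | 0.75% | 0.58% | 84.9% |
| 6, each arm | 1.56% | 1.47% | 1.63% | 90.6% |

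**5. A single result can change sides.** Pooled z-test, 15/63 v 6/63: difference 0.1429, pooled rate 21/126 = 0.1667, SE = √(0.1667 × 0.8333 × 2/63) = 0.0664, z = 2.15, one-sided p = 0.0157, not significant at 0.015. Drop three unassessed cobomarsen subjects, 15/60 v 6/63: difference 0.1548, pooled rate 21/123 = 0.1707, SE = √[0.1707 × 0.8293 × (1/60 + 1/63)] = 0.0679, z = 2.28, p = 0.0113, significant.

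**The case against.** The strongest reply is that the intended denominator is already on paper. Section 12.5.1 says all randomized subjects, section 12.4.3 speaks of subjects in the randomized period, and nothing says ORR4 will be analysed on the section 12.3.1 set. On that view the defect is a mislabelled set and a missing cross-reference. Primary-endpoint details are also deferred to a separate statistical analysis plan.

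Exclusions may well be few. The Medical Monitor confirms eligibility before randomization, dosing follows within 3 working days, an End of Treatment mSWAT is asked of everyone, and section 4.1 calls for every effort to obtain a final disease assessment. At the planned 10% rate, one cobomarsen exclusion barely moves type I error (1.56% to 1.57%). The 3.6% figure needs six of 63 lost from one arm, none from the other, and a common rate three times the one planned for vorinostat.

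The points on likely size stand: no imbalance has been shown. Nothing has been computed for the interim either, so the effect there is unquantified. The definition of ORR4 in section 12.4.3 also largely implies that a subject without a confirmed response is a non-responder. But an implied numerator does not fix the denominator, and section 12.4.1 points away from filling in missing outcomes. A later analysis plan would still have to override either section 12.3.1 or section 12.5.1, and none is among the documents supplied.

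**Conclusion.** The concern holds and should be corrected before any comparative analysis. The contradiction between sections 12.3.1 and 12.5.1 is certain from the text, as are the absence of an all-randomized set and the absence of a named primary set.

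The numerical effect is not known. It depends on how many subjects are excluded, from which arm, and how the undefined assessment is read. Equal losses do little. Unequal losses bias the comparison in either direction: with 6 assumed, from 2.2% to 3.6% type I error if they come from cobomarsen, or a fall in power from 90.6% to 84.9% if they come from vorinostat. The stated power above 80% is not shown to be wrong.

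**What to change.** - In the synopsis and section 12.3.1, define ITT as all randomized subjects, analysed in the arm to which they were randomized.
- In sections 12.4.3 and 12.4.7, name that set as the primary set for ORR4 at the final and interim analyses.
- State that any subject without a confirmed 4-month response, for whatever reason, counts as a non-responder.
- Keep the present definition as a modified-ITT sensitivity set, and specify which post-baseline assessment it requires.

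This needs wording only: no new data and no change to the 126 subjects. The price is slightly lower observed response rates. If the planned 35% and 10% are rates among assessed subjects rather than all randomized, the sponsor should check the power. With an assumed equal share excluded in each arm and counted as non-responders, continuity-corrected power is 81.7% at 5% excluded and 78.3% at 10%. Dropping the same subjects instead gives 82.4% and 79.7%, so the present definition would avoid little of that loss.
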